# 4.4 Exploratory Outcomes (Phase I)

#### 4.4.1 Questionnaire Data

Exploratory objectives of this study include determining whether nSTRIDE APS is superior to HA with regard to the endpoints in **Table 5**. Where repeated measures tests are statistically significant, tests at individual time

points will be performed. All tests will be conducted at  $\alpha$  = 0.05 and will not be adjusted for multiple comparisons as these are exploratory outcomes.

Exploratory Outcomes	Test	Expected Outcome
Mean NRS Pain Δ (1, 3, 6 Months)	Repeated Measures ANOVA	Trend APS Superior
Mean WOMAC Pain ∆ (Percent change from baseline to12 Month)	T-Test or WMW	APS Superior
Mean WOMAC Function Δ (Percent change from baseline to12 Month)	T-Test or WMW	APS Superior
Mean WOMAC Function changes over time within treatment	Repeated measures ANOVA	Significant change from baseline
Mean EQ-5D ∆ Global Assessment VAS (12 Month minus Baseline)	T-Test or WMW	APS Superior
Mean EQ-5D Δ Global Assessment VAS (Percent change from baseline to12 Month	T-Test or WMW	APS Superior
Mean EQ-5D Global Assessment VAS changes over time within treatment	Repeated measures ANOVA	Significant change from baseline
Mean EQ-5D *∆ Single Index Value (12 Month minus Baseline)	T-Test or WMW	APS Superior
Mean EQ-5D ∆ Single Index Value (Percent change from baseline to12 Month	T-Test or WMW	APS Superior
Mean EQ-5D Single Index Value changes over time within treatment	Repeated measures ANOVA	Significant change from baseline

 Table 5 – Planned Exploratory Analyses, Questionnaire Data

Exploratory Outcomes	Test	Expected Outcome
EQ-5D Dimensions (Mobility, Self-Care, Usual Activities, Pain/Discomfort, Anxiety/Depression) (12 Month)	Likelihood Ratio Chi-Square	APS Superior
Mean WOMAC Pain ∆ (1, 3, & 6 Months)	Repeated Measures ANOVA or Friedman Test	Trend APS Superior
Mean WOMAC Function Δ (1, 3, & 6 Months)	Repeated Measures ANOVA or Friedman Test	Trend APS Superior
MCID WOMAC Function Responder (1, 3, & 6 Months)	Fisher's Exact Family α = 0.05	Trend APS Superior
MCID WOMAC Pain Responder (1, 3, & 6 Months)	Fisher's Exact Family α = 0.05	Trend APS Superior
OMERACT-OARSI Responder / Non-responder** (1, 3, 6 & 12 Months) **Traditional published criteria; i.e. not including multiple restricted/ rescue medication usage between 6-12 months	Fisher's Exact Family α = 0.05	Trend APS Superior
Total Mean WOMAC Δ (1, 3, & 6 and 12 Months)	Repeated Measures ANOVA or Friedman Test	Trend APS Superior
Mean WOMAC Stiffness Δ (1, 3, & 6 and 12 Months)	Repeated Measures ANOVA or Friedman Test	Trend APS Superior
Mean EQ-5D Δ Global Assessment VAS (1, 3, & 6 Months)	Repeated Measures ANOVA or Friedman Test	Trend APS Superior

Exploratory Outcomes	Test	Expected Outcome
EQ-5D Dimensions		
(Mobility, Self-Care,		
Usual Activities,	Likelihood Ratio	Trend APS Superior
Pain/Discomfort,	Chi-Square	
Anxiety/Depression)		
(1, 3, & 6 Months)		
Mean WOMAC Pain $\Delta$		
(12 Month minus		No Site Effect
Baseline) by Treatment		No one Enect
and Site		
Mean WOMAC		
Function $\Delta$		
(12 Month minus	ANOVA	No Site Effect
Baseline) by Treatment		
and Site		
Mean WOMAC	ANOVA	Exploratory
Function $\Delta$		
(12 Month minus		
Baseline) with Usage of		
rescue medication		
within 48 hours of the		
12 month visit for knee		
OA as a covariate		
Mean WOMAC	ANOVA	Exploratory
Function $\Delta$		
(12 Month minus		
Baseline) with Usage of		
rescue medication		
within 48 hours of the		
12 month visit for any		
reason as a covariate		
Mean WOMAC	ANOVA	Exploratory
Function Δ		
(12 Month minus		
Baseline) with Usage of		
restricted medication		
within 48 hours of the		
12 month visit for knee		
OA as a covariate		

Exploratory Outcomes	Test	Expected Outcome
Mean WOMAC	ANOVA	Exploratory
Function $\Delta$		
(12 Month minus		
Baseline) with Usage of		
restricted medication		
within 48 hours of the		
12 month visit for any		
reason as a covariate		

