	bone attrition, and/or bone-on-bone contact i	ndicative of
	severe osteoarthritis/full thickness cartilage	loss), as
	confirmed by the Core Imaging Laboratory.	
	4. Body mass index \leq 40 kg/m ² .	
	 A WOMAC LK 3.1 pain subscale total score ≥ 9) and ≤ 19.
	6. Has undergone at least one prior conse	rvative OA
	treatment (e.g. physical therapy, simple analge	sics).
	7. Signed an ethics committee-reviewed and	l approved
	informed consent form.	
Exclusion Criteria:	1. Presence of clinically observed active infectio	n or severe
	inflammation in the index knee joint	or skin
	disease/breakdown or infection in the area of	the planned
	injection site of the index knee.	
	2. Presence of symptomatic OA in the non-stu	dy knee at
	screening; if unclear then the WOMAC LK 3.	1 pain sub-
	scale for the non-index knee must be \leq 5.0.	
	3. Diagnosed with rheumatoid arthritis, Reiter's	syndrome,
	psoriatic arthritis, gout, ankylosing spondylitis	, or arthritis
	secondary to other inflammatory disease	s; Human
	Immunodeficiency Virus (HIV), viral	hepatitis;
	chondrocalcinosis, Paget's disease, or	villonodular
	synovitis.	

4.	Diagnosed with leukemia, known presence of metastatic
	malignant cells, or ongoing or planned chemotherapeutic
	treatment.
5.	Disease of spine, hip or other lower extremity joints judged
	by the investigator to be contributing to the pain in the index
	knee (e.g. sciatica, nerve pain, hip OA). Note: Patients with
	contra-lateral knee replacement, or hip replacement in
	either hip, may be enrolled provided there is sufficient pain
	relief after knee replacement or hip replacement that
	analgesics are not required.
6.	Untreated symptomatic injury of the index knee (e.g., acute
	traumatic injury, anterior cruciate ligament injury, clinically
	symptomatic meniscus injury characterized by mechanical
	issue such as locking or catching).
7.	Presence of surgical hardware or other foreign body
	intended to treat arthritis or cartilage-related pathology in
	the index knee. Note: this does not include small hardware
	(e.g. screws).
8.	Presence of venous or lymphatic stasis in the index leg.
9.	Orally administered systemic steroid use within 2 weeks
	prior to screening.
10.	Planned/anticipated surgery of the index knee during the
	study period.
11.	Major surgery (e.g. osteotomy) of the index knee within 12
	months prior to screening.
12.	Minor surgery (e.g. shaving or arthroscopy) of the index
	knee within 6 months prior to screening.

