13.	A history of local anesthetic allergy.
14.	Use of systemic immunosuppressants within 6 weeks prior
	to screening.
15.	Currently on anticoagulant therapy, such as Warfarin,
	vitamin K antagonists, direct thrombin inhibitors, or factor
	Xa inhibitors or on potent anti-platelet therapy, such as
	GPIIb-IIIa antagonists Par-1 antagonists or dual anti-

	platelet therapy; i.e. an ADP receptor antagonist in
	combination with aspirin⁵.
	16 Any documented clinically significant degree of cognitive
	impairment or other condition finding or psychiatric illness
	at screening which in the oninion of the investigator could
	at screening, which, in the opinion of the investigator, could
	of the sefety and treatment effects of the study injection
	Of the salety and treatment enects of the study injection.
	17. Pregnant or nursing mothers or women planning to become
	pregnant during the time they will be participating in the
	study.
	18. Known hypersensitivity (allergy) to hyaluronan (sodium
	hyaluronate) preparations.
	19. Previously documented failed treatment with nSTRIDE APS
	or Synvisc One.
	20. Known drug or alcohol dependence currently or within the
	last year.
	21. Use of any investigational drug or device within 30 days
	prior to screening.
	22. Use of any investigational biologics within 60 days prior to
	screening.
Schedule of Visits:	Screening
	Procedure (within 28 days of screening)
	• 1 Month (± 7 days)
	• 3 Month (± 14 days)
	• 6 Month (± 14 days)
	• 12 Month (± 28 days)
	• 18 Month (± 28 days)

⁵ Subjects taking low-doses of aspirin (maximum 100 mg/day) in_**combination** with an ADP-receptor antagonist should be excluded from the study per exclusion criteria 15. A low doses of aspirin **alone** is not considered an exclusion criteria.

	• 24 Month (± 28 days)
	• 30 Month (± 28 days)
	• 36 Month (± 28 days)
	• 48 Month (± 28 days)
	• 60 Month (± 28 days)
	 Interim (when patient seeks additional intervention
	between regularly scheduled visits)
Clinical Assessment	The Western Ontario and McMaster Universities Osteoarthritis
Tools:	Index using the Likert scale, Version 3.1:
	The WOMAC LK 3.1 questionnaire is a validated tool used for
	assessing knee pain, stiffness, and function. The WOMAC LK 3.1
	has 24 items; 5 items assessing knee pain, 2 items assessing knee
	stiffness, and 17 items assessing physical function. Each item is
	answered on a 5-point Likert scale, with grading from 0 (none or

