	never) to 4 (extreme or always). A higher score indicates worse
	pain, stiffness, or functional limitation.
	The EuroQol-5 Dimensions
	The EuroQol-5 Dimensions (EQ-5D) is a validated instrument
	which assesses an individual's current health status and heath
	related quality of life. The EQ-5D-3L descriptive component
	assesses five dimensions: mobility, self-care, usual activities,
	pain/discomfort, and anxiety/depression over three levels of
	severity. The EQ visual analogue scale (EQ VAS) assesses the
	respondent's self-rated overall health state on a scale from 0 (worst
	imaginable health state) to 100 (best imaginable health state).
	Numeric Rating Scale
	The NRS is a validated measure of knee pain. The NRS is an 11
	point Likert type scale anchored by 0 "no pain" and 10 "worst
	possible pain". Subjects rate their average pain over the last 48
	hours.
	Patient Preference Questionnaire
	Patient preferences are concerned with determining patient-related
	factors such as patients' adherence to treatment, patients'

	satisfaction with treatment, and health outcomes. Patient
	preferences will be measured utilizing questions to elicit patients'
	preferences following their knee OA treatment.
	Resource Utilization and Costing
	Health economics will be evaluated throughout the study.
	Healthcare resource utilization for each subject will be recorded to
	capture information about healthcare costs following index
	treatment with nSTRIDE APS or HA and follow-up.
Imaging	Radiographs
Assessment	Standing posterior-anterior (PA) fixed flexion knee radiographs (X-
Tools:	rays) are used to assess structural features of the joint, including
	joint space width, and presence or absence of subchondral
	sclerosis, subchondral cysts, and osteophytes. X-ray assessments
	will be performed by a core imaging laboratory.
Primary Endpoint:	The primary endpoint will be the change in pain from baseline to 12
	months following injection of nSTRIDE APS or HA, as measured by
	the WOMAC LK 3.1 pain subscale.
Primary Hypothesis	H ₀ : μ _{APS} = μ _{HA} vs H ₁ : μ _{APS} ≠ μ _{HA}
Primary Hypothesis for nSTRIDE	H ₀ : μ _{APS} = μ _{HA} vs H ₁ : μ _{APS} ≠ μ _{HA}
Primary Hypothesis for nSTRIDE Superiority Testing:	H ₀ : $\mu_{APS} = \mu_{HA} vs H_1: \mu_{APS} \neq \mu_{HA}$ Where:
Primary Hypothesis for nSTRIDE Superiority Testing:	H ₀ : $\mu_{APS} = \mu_{HA} vs H_1: \mu_{APS} \neq \mu_{HA}$ Where: H ₀ is the Null Hypothesis

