# Table 9 - Planned Phase II Statistical Analysis – Health Economic Outcomes

Predictor Variable	Outcome Variable(s)	Statistic	Expected Outcome	Time points
Treatment / Crossover Group	Difference in Quality- Adjusted Life Years (QALY)	One-Way Anova	Trend APS Superior	Time of initial treatment until "failure" or end of study (Phases I and II)
Treatment / Crossover Group	Mean monthly OA-related cost for help and/or transportation	One-Way Anova	Trend APS Superior	Phase II
Treatment / Crossover Group	Mean cost per 6 months for OA-related cost for medical and/or workplace- related cost	One-Way Anova	Trend APS Superior	Phase II
Treatment / Crossover Group	Improvement in Utility Score as measured by EQ-5D Δ Single Index Value	Repeated Measures ANOVA or Friedman Test	Trend APS Superior	Time of initial treatment until "failure" or end of study (Phases I and II)
Treatment/Cr ossover	Mean cost per 6 months for	One-Way Anova	Trend APS Superior	Phase I

Group	OA-related		
	cost for		
	restricted		
	medications		

At each follow-up visit, the quality-adjusted life years (QALYs) will be calculated by multiplying the duration of time to failure (i.e. rescue medication or procedure) by a health-related quality of life (HRQoL) weight (i.e. utility score) associated with that health state. Therefore, the two key elements— HRQoL and survival—are incorporated. The EQ-5D general health state rating (scored on a scale of 0 (worst imaginable health state) to 100 (best imaginable health state)) will be used as the HRQoL weights.

In addition, the analyses will include economic cost-benefit/cost-effectiveness analyses to measure and calculate the direct and indirect cost comparison between nSTRIDE and alternative treatment options. Zimmer Biomet will rely on publicly-available, standardized datasets, such as those available from the U.S. Department of Health & Human Services, the National Center for Health Statistics and the Bureau of Labor Statistics, when conducting these analyses to help ensure outcome validity and reproducibility.

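### SAP Table 5 tests mean percent change for the EQ VAS and the EQ-5D index, where a near-zero baseline can dominate an arm's mean and a zero baseline has no value (minor; exploratory rows)

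*SAP*

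**What the plan says.** SAP Section 4.4.1, Table 5, plans a comparison of mean percent change from baseline to 12 months for two EQ-5D measures: "Single Index Value (Percent change from baseline to12 Month" and "Global Assessment VAS (Percent change from baseline to12 Month". Both rows allow a t-test or WMW and expect APS to be superior, at an unadjusted alpha of 0.05. Table 5 also tests absolute 12-month change in both measures.

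The scales are described as follows:

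- **EQ VAS.** The protocol synopsis (Clinical Assessment Tools) describes the "respondent's self-rated overall health state on a scale from 0 (worst" to 100 at best. SAP Section 4.6 gives the same range.
- **Single index.** The instrument is the EQ-5D-3L. No value set is named and no range is given. SAP Table 9 treats the index as a utility score.
- **Entry limits.** Inclusion criterion 5 ("A WOMAC LK 3.1 pain subscale total score") bounds WOMAC Pain at 9 to 19. No criterion bounds the EQ VAS or the index.

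SAP Section 4.1 has exploratory continuous variables checked by an F-test and by plots. The t-test may then give way to Satterthwaite (unequal variances) or WMW (extreme non-normality). Section 6.3.1 plans no imputation for exploratory outcomes. No passage says what to do with a zero or negative baseline.

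**The concern.** Percent change divides by the baseline, so it needs a baseline well away from zero. WOMAC Pain has one by design, but the two EQ-5D measures do not. Three things can go wrong:

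1. A very small baseline gives a value in the hundreds or thousands of percent, and that subject dominates the arm mean.
2. A zero baseline gives no value. With no imputation and no rule, the subject drops out by default.
3. If the index can be negative, the negative denominator turns an improvement into a negative percent change.

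The result would then reflect which arm happened to have the low baselines, and it could contradict the absolute-change test of the same measure in the same table.

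**Working it through.** The plan gives no figure to reproduce here. The check has two parts.

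**1. Effect of one subject.** Percent change = 100 × (month 12 − baseline) / baseline. The arm size is 93, the per-group number in SAP Section 6.1. The other 92 subjects are assumed to average +25% (index) or +20% (VAS). Arm mean = (92 × others + this subject) / 93.

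| Measure | Baseline → month 12 | Percent change | Arm mean |
|---|---|---|---|
| Index | 0.05 → 0.60 | +1100% | (2300 + 1100)/93 = +36.6% |
| Index | 0.02 → 0.60 | +2900% | (2300 + 2900)/93 = +55.9% |
| Index, if negatives are possible | −0.10 → 0.60 | −700% | (2300 − 700)/93 = +17.2% |
| Index, if negatives are possible | −0.02 → 0.60 | −3100% | (2300 − 3100)/93 = −8.6% |
| VAS | 10 → 60 | +500% | (1840 + 500)/93 = +25.2% |
| VAS | 5 → 60 | +1100% | (1840 + 1100)/93 = +31.6% |
| VAS | 2 → 60 | +2900% | (1840 + 2900)/93 = +51.0% |
| Either | 0 → any | undefined | – |

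On the absolute scale, the subject going from 0.02 to 0.60 contributes only 0.58/93 = 0.006 to the arm mean.

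**2. Power.** The documents give no EQ-5D baseline distribution, so everything below except the 93 per arm and the alpha of 0.05 is assumed (2,000 simulated trials per cell).

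- Index: baseline normal with mean 0.60 and SD 0.15, limited to 0.15–1. Change = 0.08 + 0.25 × (0.60 − baseline) + noise (SD 0.20), plus 0.09 for APS. Follow-up is limited to −0.59 to 1.
- VAS: baseline normal with mean 65 and SD 17, limited to 15–100. Change = 4 + 0.5 × (65 − baseline) + noise (SD 16), plus 7.8 for APS. Follow-up is limited to 0–100.
- A share of baselines is replaced by low values: uniform −0.20 to 0.15 (index) or 0 to 15 (VAS). Zero baselines are dropped from the percent-change tests.

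| Share of low baselines | 0% | 1% | 3% | 10% |
|---|---|---|---|---|
| Index, absolute t-test | 0.82 | 0.81 | 0.81 | 0.80 |
| Index, percent t-test | 0.71 | 0.40 | 0.17 | 0.04 |
| Index, percent WMW | 0.76 | 0.72 | 0.70 | 0.60 |
| VAS, absolute t-test | 0.80 | 0.79 | 0.79 | 0.73 |
| VAS, percent t-test | 0.64 | 0.32 | 0.11 | 0.06 |
| VAS, percent WMW | 0.72 | 0.71 | 0.69 | 0.58 |

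At 3%, the percent-change means favour the wrong arm in about 28% (index) and 26% (VAS) of trials.

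The index rows above include some negative baselines. The next table keeps every low baseline positive, at a 3% share. Set A uses a different assumed distribution. Set B is the model above with low baselines of 0.01–0.15 (index) and 1–15 (VAS).

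| 3% low, all positive | Index, A | Index, B | VAS, A | VAS, B |
|---|---|---|---|---|
| Absolute t-test | 82% | 82% | 73% | 78% |
| Percent t-test | 15% | 25% | 7% | 13% |
| Percent Satterthwaite | 15% | 25% | 6% | 13% |
| Percent WMW | 75% | 73% | 65% | 68% |
| Means reversed | 25% | 15% | 33% | 25% |

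Negative utilities are therefore not needed for the main effect. Satterthwaite does not help, because it compares the same distorted means. In set B the F-test of Section 4.1 is significant in 82% (index) and 86% (VAS) of trials, so the plan's own check would often point to Satterthwaite. The SAP does not say which replacement applies when both triggers are met.

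**The case against.** The strongest reply is that Section 4.1 already provides the remedy. Values above 1000% are plainly non-normal, both rows name WMW, and WMW brings power back to within about 7 to 11 points of absolute change at a 3% share. This stands in large part: the t-test figures are not what the trial would get if the statistician switches. However, the switch is optional and rests on reading plots, and the F-test route leads to a test that does not help. WMW also cannot rank an undefined value or put a reversed sign right.

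The second reply is that near-zero baselines may be rare or absent. The documents cannot settle that, so every magnitude here is conditional.

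Three stronger readings are tempting but not supported:

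- **That improvement can read as worsening on all these scales.** For a single subject this needs a negative baseline. The EQ VAS and WOMAC Function cannot be negative. For the index it depends on a value set that the documents do not name.
- **That the WOMAC Function percent-change row fails in the same way.** Function runs from 0 to 17 × 4 = 68 with no entry minimum, but entry requires Pain of at least 9, which makes near-zero Function unlikely. In a comparable simulation with no low baselines, percent change did as well as absolute change (0.89 against 0.87). With 3% low baselines, WMW on percent change still had 0.87 against 0.84, although the t-test fell to 0.68.
- **That the trial's conclusions are at risk.** The rows are exploratory and lie outside the fixed testing sequence.

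**Conclusion.** The concern holds for the EQ VAS and the EQ-5D index, and it is minor. The documents themselves establish that both percent-change tests are planned, that the VAS can be 0, that neither measure has an entry minimum, and that no rule covers a zero or negative baseline. The size is assumption-dependent. With 3% of baselines near zero and positive, the percent-change t-test has roughly 15–25% power for the index and 7–13% for the VAS, against about 82% and 73–78% for absolute change. WMW gives about 73–75% and 65–68%. Sign reversal for the index rests on the further assumption that the value set allows negative utilities. The practical harm is at most a misleading exploratory p-value that disagrees with the absolute-change result beside it.

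**What to change.** Delete the EQ-5D index and EQ VAS percent-change tests from Table 5, or label them descriptive with no p-value, and rely on the absolute-change tests of the same measures already in that table. If the rows are kept as descriptive summaries, name the EQ-5D-3L value set and state before unblinding how zero and negative baselines are handled. The WOMAC Pain percent-change row can stay as it is. The WOMAC Function row can stay with WMW specified as its test.

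The cost is two exploratory p-values. No data collection, sample size, or primary or secondary analysis changes.

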# Table 4 - Planned Secondary Efficacy Tests

Order of	Secondary	Test	Expected
Testing	Outcomes		Outcome
9	Mean WOMAC Pain A (12 Month minus Baseline) with Usage of rescue medication within 48 hours of the 12 month visit for any reason as a covariate	ANOVA	Exploratory
10	Mean WOMAC Pain A (12 Month minus Baseline) with Usage of restricted medication within 48 hours of the 12 month visit for knee OA as a covariate	ANOVA	Exploratory
11	Mean WOMAC Pain $\Delta$ (12 Month minus Baseline) with Usage of restricted medication within 48 hours of the 12 month visit for any reason as a covariate	ANOVA	Exploratory
12	Mean NRS Pain ∆ (12 Month minus Baseline)	T-Test or WMW	APS Superior
13	Mean WOMAC Pain changes over time within treatment	Repeated measures ANOVA	Significant change from baseline

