# 6.3 Missing Data and Sensitivity Analyses

# 6.3.1 Imputation of Missing Data in the Primary Analysis

The primary analysis will be performed on the ITT population. In the primary analysis, missing WOMAC Pain scores for subjects who are withdrawn due to reasons related to the index knee OA ("non-responders") will be considered Missing Not At Random (MNAR), and the subjects' baseline score will be carried forward in the analysis of WOMAC Pain. Scores missing for all other reasons will be considered Missing At Random and will be imputed using a Multiple Imputation method, which will replace each missing value with a set of plausible values that represent the variability around the choice of which value to impute. The monotone regression method will be used [22], and will include variables from **Table 1** (i.e. gender, age, BMI, race, and preop WOMAC Pain) as well as treatment group. As suggested in Bodner and White et al [23, 24], the number of imputations will reflect the percentage of incomplete cases. Approximately 15% attrition is estimated in the sample size calculation and thus approximately fifteen imputed datasets will be incorporated, and a seed of 20190516 will be used in generating the random numbers.

No imputation of missing values is planned for secondary or exploratory outcome variables.

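### Six exploratory rows offer the Friedman test, which cannot compare APS with HA, as an alternative to a repeated-measures ANOVA that is itself unspecified

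*SAP*

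**What the plan says.** SAP section 4.4.1 gives the question that the rows are meant to answer: "Exploratory objectives of this study include determining whether nSTRIDE APS is superior to HA with regard to the endpoints in" Table 5. Five rows of that table then list "Repeated Measures ANOVA or Friedman Test" and expect a trend in favour of APS:

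- WOMAC Pain, WOMAC Function and EQ-5D VAS, each at months 1, 3 and 6;
- Total WOMAC and WOMAC Stiffness, each at months 1, 3, 6 and 12.

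Table 9 (section 4.6) lists the same pair of tests for the EQ-5D single index value. The predictor there is the four-level treatment/crossover group defined in section 4.5, and the expected outcome is the same.

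Section 4.4.1 also sets a gate: "Where repeated measures tests are statistically significant, tests at individual time" points follow. All Table 5 tests are run at 0.05 and "will not be adjusted for multiple comparisons as these are exploratory outcomes".

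On non-parametric alternatives, section 4.1 lets t-tests be replaced by the Satterthwaite or Wilcoxon Mann-Whitney (WMW) test. It says nothing about when Friedman replaces ANOVA.

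On missing data, section 6.3.1 states: "No imputation of missing values is planned for secondary or exploratory outcome variables". The per-protocol definition in section 6, which covers secondary and exploratory efficacy, says that such analyses take whatever data the subjects have.

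**The concern.** The rows ask whether APS does better than HA. One of the two permitted tests cannot answer that, because it makes no use of treatment assignment. Two errors follow. If both arms drift in the same way across visits, Friedman can be significant in a row labelled as expecting APS to do better, and the result can be misread as superiority. If APS is better by a steady amount at every visit, Friedman will not see it. Because section 4.4.1 makes visit-level tests depend on a significant repeated-measures result, the first error can open those tests and the second can keep them shut.

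The SAP's own expectations make the first error realistic. Section 6.3.2 says that the APS–saline difference stays small until some time after month 6, and section 6.1 assumes that HA performs like saline. Three of the five Table 5 rows stop at month 6, where little separation between arms is expected but a shared time course is quite possible.

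The other permitted test is only a name. The SAP does not say which terms the repeated-measures ANOVA contains, which term has to be significant, what covariance structure is used, or what happens to a subject with a missed visit.

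**Working it through.** **1. What Friedman uses.** For subject *i* with scores *y(i,1), …, y(i,k)* at *k* visits, the test ranks the *k* scores within that subject, sums the ranks for each visit over all subjects, and asks whether those sums differ. Adding a constant *c* to all of a subject's scores leaves that subject's ranks unchanged. Two results follow.

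- An arm difference that is the same at every visit adds a constant to each subject in one arm. It changes no rank, so the statistic does not move.
- Subtracting baseline also changes no rank. As the rows are labelled, baseline is not one of the ranked visits, so the test compares the listed follow-up visits with each other.

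Running Friedman separately in each arm does not help. It gives two within-arm results and no comparison between them.

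**2. Simulation.** Inputs from the SAP: 123 per arm and a difference of 2.27 points (section 6.1, Table 15), and alpha 0.05 (section 4.4.1). Assumed: three visits, and between- and within-subject SDs of 2.9 each, so that the total SD is √(2.9² + 2.9²) = 4.10, close to the 4.06 in Table 15. There were 2,000 simulated trials per scenario. The comparator is the between-arm test of a two-arm repeated-measures ANOVA, which equals a t-test on subject means.

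| Scenario | Friedman rejects | Between-arm test rejects |
|---|---|---|
| Arm difference 2.27 at every visit, no time trend | 4.6% | 100% |
| No arm difference, shared drift of 0, −0.5, −1.0 | 82% | 5.7% |
| Neither | 4.8% | 4.2% |

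Shifting one whole arm by a further constant left the Friedman p-value unchanged in every simulated trial, as step 1 requires. The 82% depends on the assumed drift and SDs. The failure to respond to a constant arm difference does not.

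**3. Which rows are affected.** Friedman appears in the five Table 5 rows and the one Table 9 row listed above. The row "Mean NRS Pain Δ (1, 3, 6 Months" lists ANOVA only. Rows such as "Mean WOMAC Function changes over time within treatment" are within-arm by design.

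**4. Missed visits under a classical ANOVA.** A classical fit without imputation keeps only subjects with every visit. If visits are missed independently at rate *m*, the number complete over *k* visits is 246 × (1 − *m*)^*k*. The documents give no per-visit rate, so *m* is assumed.

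| *m* | 3 visits | 4 visits |
|---|---|---|
| 2% | 232 | 227 |
| 5% | 211 | 200 |
| 10% | 179 | 161 |

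For example, 246 × 0.95³ = 246 × 0.857 = 211. These figures start from all 246 planned subjects, whereas the analyses use the per-protocol population. They show sensitivity and do not forecast a loss. A mixed-model fit would keep the partial records.

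**The case against.** The best defence is that Friedman is only an alternative. A repeated-measures ANOVA with an arm term would answer the question, and nothing obliges the analyst to use Friedman. Table 5 also plans between-arm Fisher tests of responders at months 1, 3 and 6. A visit-level test opened wrongly by the gate would, if it compares arms, still be a valid comparison at that visit. Everything here is exploratory, and the primary endpoint has its own t-test with multiple imputation. All of this stands, and it limits the severity. It does not rescue the Friedman option: the plan permits it with no selection rule, and under it the stated expected outcome cannot be tested.

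On the ANOVA, a reader might infer that it drops every subject with a missed visit. The documents do not support that. Listwise deletion belongs to the classical fit, and the SAP does not say which fit is meant. Declining to impute does not imply deletion, and the per-protocol wording on available data points away from it without settling the matter.

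A reader might also put the loss at 49 to 62 subjects or more (0.20 × 246 = 49; 0.25 × 246 = 62). Those rates are the protective allowance in section 6.1. Section 6.3.1 estimates about 15%, or 0.15 × 246 = 37. Neither is a per-visit rate, and a subject lost after month 6 is still complete for the three rows that end there. No minimum loss can be derived.

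Finally, Table 4 step 13, "Mean WOMAC Pain changes over time within treatment", may look like another instance. It is not: it is a within-arm test with no Friedman option.

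**Conclusion.** The Friedman option is wrong as written in six rows: five in Table 5 and one in Table 9. This follows from how the test is built and needs no assumption about the data. A shared time trend could be read as APS superiority and could open the visit-level tests, while a steady arm difference would be missed. The lack of any rule for choosing Friedman leaves the choice open once data are seen.

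The repeated-measures ANOVA is underspecified rather than wrong. If fitted classically without imputation, it would discard subjects with a missed visit, which sits badly with the SAP's statement on available data. The number lost cannot be stated from the documents.

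The consequence is confined to exploratory, unadjusted analyses. No sample-size figure changes and the primary result is untouched. The correction should still be made, because it is cheap and the rows cannot otherwise be relied on to support the claim attached to them.

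**What to change.** Delete Friedman from all six rows.

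**Table 5.** Name a mixed model for repeated measures with arm, visit, arm-by-visit and baseline value. Base both the APS–HA conclusion and the trigger for visit-level tests on the arm and arm-by-visit terms, not on the visit term. As the non-parametric fallback, use a WMW test between arms at each visit, and state when it applies by extending the section 4.1 rule to these rows.

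**Table 9.** Use the same model with the four-level treatment/crossover group in place of arm, since a single APS–HA contrast does not fit that predictor. As the fallback, use a between-group rank test at each visit, such as Kruskal-Wallis.

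The cost is SAP wording and standard software, with no new data. The mixed model assumes that data are missing at random. Section 6.3.1 treats withdrawals related to index-knee OA as not missing at random for the primary outcome, so the model will not by itself remove bias from those withdrawals, and the SAP should say so.
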